6.2. Efficacy

Collection of platelet counts on week 1 (pre-dose), week 2, monthly during year 1, every two months during year 2, and every 3 months during years 3-6, along with platelet function studies. Bleeding symptoms will be monitored by bleeding score assessments.

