Treatment will be initiated at Cornell. Patients will be seen either at Cornell or by a their local doctor 1-3 months thereafter. A recently developed bleeding score, designed to incorporate the four leading bleeding scores, will be administered on study visits to semi-quantitatively assess bleeding.¹⁴ The Page bleeding score is completed using the information from this questionnaire. The hypothesis is that patients with Wiskott-Aldrich Syndrome will have more bleeding at given platelet counts than will patients with ITP. Furthermore the degree of bleeding will correlate not only with the platelet count but with the degree of platelet dysfunction. Platelet size will be explored also. We anticipate the platelet function and bleeding scores will improve with the institution of Promacta therapy if the

platelet counts increase. Even if some of these changes in bleeding are small, the overall direction will help to clarify the effect of treatment on these scores.

There is no placebo; thus, patients will be compared to themselves descriptively before and after treatment through complete physical examinations, complete blood draws, urinalysis, and platelet studies.

[name] has an appointment at Memorial Sloan Kettering, so a patient initiated at Cornell can be followed with appropriate testing at the MSKCC site. In addition, a patient who comes to the Cornell site to provide consent and initiate treatment may be followed at another site for local Laboratory Testing.

Urinalysis, Admission Panel (including liver tests), CBC with Platelet and Differential, PT/PTT, PFA, Fibrinogen, D-Dimers, Platelet Function Analysis, Immature Platelet Fraction (Platelet Reticulocyte Count), and Single Platelet Flow Cytometry will be assessed.

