5. STUDY TREATMENTS

5.1. Treatment Assignment

1) Review of subject’s medical history
	
2) A routine physical examination, including collection of subject’s height, weight, temperature, blood pressure, and pulse rate, and a review of all medicines
	
3) The study doctor will assess subject’s bruising and bleeding by physical examination and by asking questions. He/she will do this by using the Page ITP Bleeding Score.
 
4) At Screening, about 10-20 mL of blood will be drawn to conduct laboratory tests.
	
5) The starting dose will be based upon weight; patients over 50 kg will start at 50mg daily unless they are of East Asian origin in which case they will use 25 mg as their initial dose. The dose of eltrombopag will be titrated for each subject based on their platelet response. Eltrombopag starting doses for children <50 kg will be scaled by body weight and the starting

--	---	--	---

	that a subject is taking.		dose will be approximately 2mg/kg once daily.
--	---------------------------	--	---

Note: See schedule of events on page 25

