8.3.1.1. Efficacy Analyses

Primary endpoint will be increasing platelet counts in WAS/XLT patients to above 50,000/ul. The generalizability of the data will depend upon including both WAS and XLT patients but no specific distribution of patients within these 2 groups is pre-specified. The proportion of patients showing this increase will be summarized with 95% confidence intervals. The proportion of patients maintaining this increase will be summarized for time points of interest.

Correlations will be evaluated graphically. In addition, Spearman rank correlation coefficients may be used to evaluate the association of platelet count and bleeding score, at each visit.

Any within-subject analyses may be based on Wilcoxon signed rank tests.

Secondary endpoints will involve reduction of bleeding in treated patients within 12 weeks, and to specifically examine the reduction in bleeding in those with platelet counts > 100,000/ul and also > 50,000/ul.

We anticipate that platelet function will improve as the platelet count increases but not normalize.

Therefore efficacy will depend on platelet counts, immature platelet fraction, platelet function by flow cytometry, and the bleeding score. Since the dose required may vary from patient to patient and may only be changed every 2 weeks, a platelet count > 50,000/ul at any time within the first 12 weeks will be considered a response. Similarly, secondary endpoints involving reduction in bleeding and improvement in platelet function will also be explored within a 4 to 12 week window for assessment.

Toxicity will depend upon adverse events, abnormal liver tests, and other abnormal findings.

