

SCHEDULE OF EVENTS
“Pathobiology of Thrombocytopenia and Bleeding in Patients with Wiskott-Aldrich Syndrome.” Protocol #: 0801009600

	Screening	Day 1/Baseline	Week 2	Week 4	Months ⁴ 2 – 12	Months ⁵ 14 - 24	Months ⁶ 27 - 72
Evaluation and Management							
Informed Consent	x						
Bleeding Score ¹	x	x	x	x	x	x	x
Standard of Care							
Physical Examination	x	x	x	x	x	x	x
Urinalysis	x						
Admission Panel (Includes liver tests such as ALT, AST, bilirubin)	x	x	x	x	x	x	x
CBC with Platelet and Diff	x	x	x	x	x	x	x
Diagnostic Tests for Platelet Function							
PT/PTT	x						
D-Dimers	x						
Fibrinogen	x						
PFA ²					x		
Immature Platelet Fraction (Platelet Reticulocyte Count) ³	x	x	x	x	x	x	x
Single Platelet Flow Cytometry ⁷	x			x	x ⁸		

1. The Page bleeding score will be administered at each visit in order to semi-quantitatively assess bleeding
2. PFA (Platelet function Analysis) will be assessed once for WAS/XLT patients and control patients at month 2, provided platelet count is >50 k
3. IPF will be obtained with each Cornell in-clinic CBC where possible
4. Subjects will have their blood drawn monthly and be seen every 3 months during the first year
5. Subjects will have their blood drawn every 2 months and be seen every 4 months in the second year
6. Subjects will have their blood drawn every 3 months and be seen every 6 months in the 3rd – 6th years
7. Single Platelet Flow Cytometry tests will be performed by [name] at screening, once between months 1-3, and once after 1-2 years on study.

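### After screening, nothing keeps the doctor who gives the Page bleeding score from knowing that visit's platelet count, although the plan relates the two

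*Combined protocol and SAP*

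**What the plan says.** **How bleeding is scored.** Section 5.1, step 3: "The study doctor will assess subject’s bruising and bleeding by physical examination and by asking questions", using the Page score. Section 3.1 adds that the score is completed from a questionnaire. Schedule of Events, footnote 1: "The Page bleeding score will be administered at each visit in order to semi-quantitatively assess bleeding". Section 6.2 gives no procedure beyond "Bleeding symptoms will be monitored by bleeding score assessments".

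**Timing relative to the count.** In the Schedule, the bleeding score and the CBC are both marked in every column from screening to months 27-72. In 5.1, the screening blood draw is step 4, after the score. No other text bears on the order of the two, and none mentions masking the scorer or using an independent assessor.

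**Control and expectation.** Section 3.1: "There is no placebo; thus, patients will be compared to themselves descriptively before and after treatment". The same section states the expected direction: "We anticipate the platelet function and bleeding scores will improve with the institution of Promacta therapy if the" counts go up. It also hypothesises that the degree of bleeding will correlate with the platelet count.

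**Use of the score.** Section 8.3.1.1: "Secondary endpoints will involve reduction of bleeding in treated patients within 12 weeks", with the reduction examined specifically in patients above 100,000/ul and above 50,000/ul. It also says "Spearman rank correlation coefficients may be used to evaluate the association of platelet count and bleeding score, at each visit".

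**The concern.** The Page score is partly a graded judgement. A scorer who has just seen a high count, and works under a protocol that predicts less bleeding at higher counts, may grade borderline bruising down; a low count may push the other way. The score then carries some of the count's information, and correlating the two partly correlates the count with itself.

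Two planned results are directly at risk: the same-visit association of count and bleeding, and the bleeding reduction in patients above the two count thresholds. They bear on the hypothesis in 3.1 and on whether a higher count means less bleeding in these patients. The bias enters when the score is recorded. Medians, graphs, rank correlations and signed-rank tests all inherit it, and nothing recorded under the present plan would show which scores were given with the count known.

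**Working it through.** **1. The plan's own figure.** Section 8.2.1 says that 0 responders among 15 makes a true response rate above 20% unlikely. The one-sided 95% upper limit is 1 - 0.05^(1/15) = 18.1%, and the rule of three gives 3/15 = 20%, so the statement reproduces. It concerns the platelet response, a laboratory value. Neither the concern nor the fix changes it. The documents give no SD, effect size or error rate for the bleeding score.

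**2. Is the scorer kept from the count?**

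| Place | Score and count |
|---|---|
| 5.1, steps 3 and 4 | score listed before the screening blood draw |
| 5.1, later visits | nothing stated |
| 6.2 | score used; no order, no masking |
| Schedule of Events, footnote 1 | score at each visit; no order relative to the CBC |
| 8.3.1.1 | same-visit count and score related to each other |

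The gap therefore begins after screening.

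**3. Size of a spurious association.** Assumptions: true bleeding is unrelated to the count; n = 15; count and unbiased score are standard normal; knowing the count changes the score by -b SD per SD of count. Then:

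- Pearson correlation: r = -b / sqrt(1 + b²).
- Expected sample Spearman: [6 / (π(n + 1))] × [arcsin r + (n - 2) arcsin(r/2)].

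| b (assumed) | r | Expected Spearman, n = 15 |
|---|---|---|
| 0 | 0 | 0 |
| 0.2 | -0.196 | -0.176 |
| 0.3 | -0.287 | -0.26 |
| 0.5 | -0.447 | -0.41 |

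For b = 0.5: 6/(16π) = 0.1194; arcsin(0.447) = 0.464; 13 × arcsin(0.2236) = 2.932; 0.1194 × (0.464 + 2.932) = 0.41. Simulation of 6,000 runs gave -0.17, -0.26 and -0.41 for the three non-zero values.

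A second simulation (3,000 runs) let 5 in 8 patients respond, as in the preliminary data in 1.2, with an assumed count rise of 2 baseline SDs. That spreads follow-up counts more widely, so the same b acts more strongly: mean Spearman -0.13, -0.30 and -0.53 for b = 0.10, 0.25 and 0.50, against 0.01 for b = 0.

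**4. Size of a spurious reduction in patients whose counts rise.** If both scores are given with the count known, the false change is -b × (rise in count, in SDs). For b = 0.2 to 0.5, a rise of 1 SD gives -0.2 to -0.5 SD of score, and a rise of 2 SD gives -0.4 to -1.0 SD. Over all patients with 5/8 responding, b = 0.25 and a 2 SD rise, this is 0.25 × 2 × 5/8 = 0.31 SD; the second simulation also gave 0.31.

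**5. What hiding the count cannot remove.** In the second simulation, a shift of 0.25 or 0.50 SD applied to every patient, merely because treatment is known, left the mean Spearman at 0.00 but produced a mean bleeding change of -0.25 or -0.50 SD. Expectation about treatment acts on the before-after change, and knowledge of the count acts on the association. Scoring before the count is known addresses the second.

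**The case against.** **The documents do not say the scorer knows the count.** True. They are silent after screening, and the one ordering they contain, in 5.1, runs the protective way. A reader might infer that scores will be given with the count in hand; the text does not support that. It leaves the possibility open and unrecorded.

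**The before-after reduction has larger threats.** This stands. With no placebo, doctor, patient and parent know that treatment has started. Under Schedule footnote 4, year-1 bloods are monthly but patients are seen every 3 months, so earlier counts may be known, and doses are titrated on counts. The score also draws on a questionnaire, and an informant is not masked by hiding a result from the doctor. A reader might infer that same-day counts could explain the whole bleeding reduction, or that the fix would make it unbiased. Neither follows.

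**The analysis is exploratory.** Also true. Section 8.3.1 calls for descriptive summaries, the Spearman and Wilcoxon methods are optional, and no significance level is set. It would be wrong to speak of a formal error rate being exceeded, so none is claimed here. A biased score nevertheless distorts a descriptive coefficient or plot just as much.

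**The primary endpoint is untouched.** Correct: it is a laboratory platelet count.

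**Conclusion.** The concern holds in a limited form. After screening, the plan allows that visit's platelet count to influence the score it is then related to. This can create or inflate the same-visit association and the bleeding summaries above 50,000 and 100,000/ul.

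Under an assumed bias of 0.2 to 0.5 SD of score per SD of count, the mean Spearman coefficient with 15 patients would be about -0.17 to -0.41 with no true association. That range is only as good as the assumed bias, and a wider spread of counts makes it larger. The overall before-after reduction is partly affected, and the primary endpoint is not. This is a cheap improvement worth making, not a flaw that undermines the study.

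**What to change.** 1. In 6.2 and Schedule footnote 1, state that at each visit the Page score is completed and signed before that visit's platelet count is available to the scorer. Apply this also at the local or other follow-up sites that 3.1 allows.
2. Add a yes/no CRF item recording whether the scorer knew that visit's count. Where the order cannot be kept, the score is still given and marked accordingly.
3. In 8.3.1.1, repeat the same-visit correlation and the >50,000 and >100,000/ul bleeding summaries without scores given with the count known, showing the number of patients left.
4. State in the report that treatment and earlier counts were known to the scorer, so the before-after reduction remains open to expectation.

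Cost: a short written procedure covering all sites, two sentences of protocol text, one CRF item and one repeated set of summaries. It needs no extra staff, visit, blood or patients. The repeated summaries may rest on few patients if many scores are given with the count known.

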6.3. Safety

This protocol is investigator initiated. The Principal Investigator is responsible for the study and will monitor the safety of the patients on the protocol.

The following safety will be reviewed by the Principal Investigator:

- Physical Exam
- Vital Signs
- Laboratory results (blood count, liver function tests, reticulocyte count, urine tests)
- SAE and AE events
- Bone marrow aspirations/biopsies (if relevant)

Adverse Events (AEs) will be graded according to Common Terminology Criteria for Adverse Events v4.03(CTCAE)The PI will determine the relationship of AEs to the test procedure/device/agent as not related, possibly related, probably related or definitely related, using standard criteria for clinical trials. Interim assessment of AEs will be conducted semi-annually by the data safety monitoring board.

Note: All serious adverse events will be followed until resolution of the events or definitive conclusion.

Hepatotoxicity

Administration of eltrombopag may cause hepatotoxicity. In the controlled clinical ITP studies, serum liver test abnormalities (predominantly Grade 2 or less in severity) were reported in 10% and 8% of the PROMACTA and placebo groups, respectively. Two patients (1%) treated with PROMACTA and two patients in the placebo group (3%) discontinued treatment due to hepatobiliary laboratory abnormalities. Seven of the patients treated with PROMACTA in the controlled studies with hepatobiliary laboratory abnormalities were re-exposed to PROMACTA in the extension study. Six of these patients again experienced liver test abnormalities (predominantly Grade 1) resulting in discontinuation of PROMACTA in one patient. In the extension study, one additional patient had PROMACTA discontinued due to liver test abnormalities (\leq Grade 3).

Serum ALT, AST, and bilirubin will be measured prior to initiation of PROMACTA, every 2 weeks during the dose adjustment phase and monthly following establishment of a stable dose. If bilirubin is elevated, perform fractionation. Evaluate abnormal serum liver tests with repeat testing within 3 to 5 days. If the abnormalities are confirmed, monitor serum liver tests weekly until the abnormality(ies) resolve, stabilize, or return to baseline levels. Discontinue PROMACTA if ALT levels increase to $\geq 3X$ the upper limit of normal (ULN) and are:

- Progressive, or
- Persistent for ≥ 4 weeks, or
- Accompanied by increased direct bilirubin, or
- Accompanied by clinical symptoms of liver injury or evidence for hepatic decompensation.

Bone Marrow Reticulin Formation and Risk for Bone Marrow Fibrosis

Eltrombopag is a thrombopoietin (TPO) receptor agonist and TPO-receptor agonists may increase the risk for the development or progression of reticulin fiber deposition within the bone marrow.

In the ITP extension study, seven patients had reticulin fiber deposition reported in bone marrow biopsies, including two patients who also had collagen fiber deposition. The fiber deposition was not clearly associated with cytopenias and did not necessitate discontinuation of eltrombopag. However, clinical studies have not yet excluded a risk of bone marrow fibrosis with cytopenias and discontinuation of eltrombopag.

Prior to initiation of eltrombopag, examine the peripheral blood smear closely to establish a baseline level of cellular morphologic abnormalities. Following identification of a stable dose of eltrombopag, examine peripheral blood smears and CBCs monthly for new or worsening morphological abnormalities (e.g., teardrop and nucleated red blood cells, immature white blood cells) or cytopenia(s). If the patient develops new or worsening morphological abnormalities or cytopenia(s), discontinue treatment with eltrombopag and consider a bone marrow biopsy, including staining for fibrosis.

Worsened Thrombocytopenia After Cessation of Eltrombopag

Discontinuation of eltrombopag may result in thrombocytopenia of greater severity than was present prior to therapy with eltrombopag although this is only seen in a minority of patients who stop the drug. This worsened thrombocytopenia may increase the patient's risk of bleeding, particularly if

eltrombopag is discontinued while the patient is on anticoagulants or antiplatelet agents. In the controlled ITP clinical studies, transient decreases in platelet counts to levels lower than baseline were observed following discontinuation of treatment in 10% and 6% of the eltrombopag and placebo groups, respectively. Serious hemorrhagic events requiring the use of supportive ITP medications occurred in 3 severely thrombocytopenic patients within one month following the discontinuation of eltrombopag; none were reported among the placebo group.

Following discontinuation of eltrombopag, obtain weekly CBCs, including platelet counts for at least 4 weeks and consider alternative treatments for worsening thrombocytopenia, according to current treatment guidelines

History of Thromboembolic Events

Thrombotic events can occur at any platelet count. Thrombotic/thromboembolic complications may result from excessive increases in platelet counts. Excessive doses of eltrombopag or medication errors that result in excessive doses of eltrombopag may increase platelet counts to a level that produces thrombotic/thromboembolic complications. In the controlled ITP clinical studies, one thrombotic/thromboembolic complication was reported within the groups that received eltrombopag and none within the placebo groups. Seven patients experienced thrombotic/thromboembolic complications in the ITP extension study.

Caution should be used when administering eltrombopag to patients with known risk factors for thromboembolism (e.g., Factor V Leiden, ATIII deficiency, antiphospholipid syndrome, etc.).

Malignancies and Progression of Malignancies

Stimulation of the TPO receptor on the surface of hematopoietic cells by eltrombopag may increase the risk for hematologic malignancies. In the controlled ITP clinical studies, patients were treated with eltrombopag for a maximum of 6 weeks and during this period no hematologic malignancies were reported. One hematologic malignancy (non-Hodgkin's lymphoma) was reported in the ITP extension study.

Cataracts

Cataracts were observed in toxicology studies of eltrombopag in rodents (see Non-clinical Information). The clinical relevance of this finding continues to be evaluated in all ongoing NOVARTIS sponsored clinical studies. To date, there is however, no evidence that eltrombopag increases the incidence nor progression of cataracts in patients who have received eltrombopag. In the controlled ITP clinical studies, cataracts developed or worsened in five (5%) patients who received 50 mg eltrombopag daily and two (3%) placebo-group patients. In the ITP extension study, cataracts developed or worsened in 4% of patients who underwent ocular examination prior to therapy with eltrombopag. A significant proportion of patients in the ITP clinical studies were also exposed to chronic corticosteroid administration.

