4. SUBJECT SELECTION AND WITHDRAWAL CRITERIA

4.1. Number of Subjects:

25 WAS/XLT Patients (10 of whom will have a blood draw only) + 10 Normal Control Patients = 35 Total Patients

4.2. Inclusion Criteria:

In order to be eligible for study entry, subjects must comply with the following:

- Males or females from 3 months to 80 years old
- Signed written informed consent obtained prior to study entry
- Clinical diagnosis of WAS or XLT
- Platelet levels less than $75 \times 10^9/L$
- Adequate renal and hepatic function (creatinine and bilirubin less than or equal to $1.5 \times ULN$, AST and ALT less than or equal to $2.5 \times ULN$)

4.3. Exclusion Criteria:

Any patient is ineligible for study entry if he/she:

- Over the age of 80
- Pregnant or lactating women
- Fertile men who are not practicing or who are unwilling to practice birth control while enrolled in the study or until at least 6 months after treatment

- Aspirin, aspirin-containing compounds, salicylates, non-steroidal anti-inflammatory medications (NSAIDS), clopidogrel or ticlopidine, warfarin or other vitamin K antagonists, unfractionated or low molecular heparin within 7 days of first treatment
- Red blood cell transfusion in the past four weeks
- Elevated ($> 1.5 \times$ ULN) prothrombin time (PT) or partial thromboplastin time (PTT)
- New York Heart Classification III or IV heart disease. Other severe cardiovascular or cardiopulmonary disease, including COPD.
- Known HIV infection, hepatitis B or C infection
- Any infection requiring antibiotic treatment within 3 days
- Other concurrent medical or psychiatric conditions that, in the Investigator's opinion, may be likely to confound study interpretation or prevent completion of study procedures and follow-up examinations.
- Prior malignancy with less than a 5-year disease-free interval, excluding nonmelanoma skin cancers and carcinoma in situ of the cervix

Eligibility criteria for controls:

- a) Within 5 years of the age of the enrolled patient
- b) No overt hematologic diagnosis
- c) Male

4.4. Withdrawal Criteria:

1. Treatment with eltrombopag should be discontinued because of abnormal liver tests if any of the following 4 conditions apply:

- ALT levels ≥ 3 times upper limit of normal (ULN) and bilirubin levels > 1.5 times ($> 35\%$ conjugated bilirubin) ULN,
- (2) ALT levels ≥ 3 times ULN and appearance or worsening of hepatitis symptoms or rash,
- (3) ALT levels remain ≥ 3 times ULN for ≥ 4 weeks, or

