- (4) ALT levels are ≥ 5 times ULN.
- If a subject has an adverse experience that would, in the investigator's judgment, make continued participation in the study an unacceptable risk
- Note: If the subject's ALT and bilirubin levels decrease so that both are < 1.5 times ULN, the

investigator may decide to restart the medication and monitor on a weekly basis.

- Study medications will be discontinued in the event of any thrombosis

If subject’s platelet count goes above 200,000, the dose of study medication will be reduced.

As indicated on page 5, perhaps 2-3 of the 15 patients in the study might be at risk over a lifetime for a malignancy such as lymphoma, but it is not very likely to happen during the relatively short time course of the study. If 1 patient develops another type of malignancy or 2 patients develop a Non-Hodgkin Lymphoma during the course of the study, the study will be stopped. Prior to the study being restarted (if this is the desire of the investigators), there will be a formal request to re-open the study submitted to the FDA with a letter of support from Novartis.

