6. STUDY ASSESSMENTS AND PROCEDURES

6.1. Critical Baseline Assessments

Complete Blood Counts (CBCs)

CBCs, including platelet counts and peripheral blood smears, will be monitored prior to initiation, throughout, and following discontinuation of therapy with PROMACTA. Prior to the initiation of PROMACTA, the peripheral blood differential will be examined to establish the extent of red and white blood cell abnormalities. CBCs, including platelet counts and peripheral blood smears, will be obtained weekly during the dose adjustment phase of therapy with PROMACTA and then monthly following establishment of a stable dose of PROMACTA. CBCs, including platelet counts will be obtained weekly to biweekly for at least 4 weeks following discontinuation of PROMACTA.

Liver tests

Serum liver tests (ALT, AST, and bilirubin) will be monitored prior to initiation of PROMACTA, every 2 weeks during the dose adjustment phase and monthly following establishment of a stable dose. If bilirubin is elevated, fractionation will be performed. If abnormal levels are detected, the tests will be repeated within 3 to 5 days. If the abnormalities are confirmed, serum liver tests will be monitored weekly until the abnormality(ies) resolve, stabilize, or return to baseline levels. PROMACTA will be discontinued based on the stopping rules outlined in section 6.3.1

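### Section 6.3 conflicts with the list in sections 4.4 and 6.3.1 on when an individual patient's eltrombopag is discontinued for liver test abnormalities

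*Combined protocol and SAP*

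**What the plan says.** All references are to the combined protocol and SAP.

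- **Section 6.3 (Safety, Hepatotoxicity).** The instruction begins "Discontinue PROMACTA if ALT levels increase to" 3 times ULN or more. It applies when the rise is progressive, when it lasts four weeks or longer, when it is "Accompanied by increased direct bilirubin, or" when there are symptoms of liver injury or signs of decompensation.
- **Section 4.4 (Withdrawal Criteria).** There are four conditions. The first is "ALT levels ≥ 3 times upper limit of normal (ULN) and bilirubin levels > 1.5 times" ULN, with more than 35% conjugated. The second is "2) ALT levels ≥ 3 times ULN and appearance or worsening of hepatitis symptoms or rash". The third is "3) ALT levels remain ≥ 3 times ULN for ≥ 4 weeks, or" and the last is "4) ALT levels are ≥ 5 times ULN". A note lets the investigator restart once ALT and bilirubin are both below 1.5 times ULN.
- **Section 6.3.1 (Liver chemistry stopping and follow-up criteria).** This is the same four-item list as 4.4 with different signs: bilirubin at or above 1.5 times ULN, duration longer than four weeks, and restart at or below 1.5 times ULN.
- **Section 6.1.** "PROMACTA will be discontinued based on the stopping rules outlined in section 6.3.1".
- **Study-level rule.** Section 4.4.1, rule 4, stops the study when 33% of patients reach the individual withdrawal criteria for liver events. Section 6.3.1 also states a 33% stop, but on its own list.

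**The concern.** An individual discontinuation rule has to give one answer for one set of laboratory values. Here the answer depends on the section consulted, and the disagreement runs in both directions, so following one version does not satisfy the other.

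Two things are at stake. The first is exposure during a liver test abnormality. A wrong decision either way has a cost in the protocol's own terms, because section 6.3 also describes worsened thrombocytopenia and serious bleeding after the drug is stopped. The second is the reported number of liver discontinuations, which cannot be reproduced if the criterion is not unique. Section 3.1 expects about 80% of the treated patients to be children. Section 3.1 also allows follow-up by a local doctor or at another site, and section 9.2 foresees no study monitoring, so a difference in reading could go unnoticed.

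**Working it through.** The plan states no figure on this point, so there is nothing to reproduce first. The check sets the printed rules side by side and applies them to constructed patients.

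**Step 1. The rules** (ALT and bilirubin in multiples of ULN)

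| Criterion | 6.3 | 4.4 | 6.3.1 |
|---|---|---|---|
| ALT ≥3 and progressive | stop | not listed | not listed |
| ALT ≥3 with bilirubin | any increase in direct bilirubin | >1.5, with >35% conjugated | ≥1.5, with >35% conjugated |
| ALT ≥3, duration | ≥4 weeks | ≥4 weeks | >4 weeks |
| ALT ≥3, clinical picture | liver-injury symptoms or decompensation | hepatitis symptoms or rash | hepatitis symptoms or rash |
| ALT alone | not listed | ≥5 | ≥5 |
| Restart | not stated | both <1.5 | both ≤1.5 |

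**Step 2. Four constructed patients** (no other feature present in any of them)

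| Patient | 6.3 | 4.4 | 6.3.1 |
|---|---|---|---|
| ALT 3.2, then 3.8, then 4.5 within four weeks | met | not met (4.5 < 5) | not met |
| ALT 3.5, direct bilirubin raised, total 1.2 | met | not met (1.2 < 1.5) | not met |
| Single ALT of 6, neither progressive nor persistent | not met | met (6 ≥ 5) | met |
| ALT 3.5 with rash only | not met | met | met |

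Two patients meet only 6.3 and two meet only the other list. The first row takes successive rises as progressive, a term the protocol does not define. The fourth row takes rash alone not to be a symptom of liver injury, since 6.3 does not name it.

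**Step 3. Boundary differences and the 33% count.** Section 3.1 gives 15 treated patients. 0.33 × 15 = 4.95, so 5 patients trigger the stop. Suppose four patients meet both lists, and a fifth has ALT 3.2 for exactly four weeks and then falls below 3.

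- Counted on 4.4: 5/15 = 33.3%, which reaches 33%.
- Counted on 6.3.1: 4/15 = 26.7%, which does not.

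A patient with ALT 3.2 and bilirubin of exactly 1.5, 40% conjugated, goes the other way: counted on 6.3.1 but not on 4.4. This step reads the withdrawal criteria in rule 4 of 4.4.1 as those of section 4.4.

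**Step 4. How likely is the exact four-week case?** Sections 6.1 and 6.3 require a repeat test within 3 to 5 days, then weekly tests once the abnormality is confirmed. If the weekly tests run from the repeat (an assumption), they fall on days 3–5, 10–12, 17–19, 24–26 and 31–33 after the first raised value. None falls on day 28, and the day 31–33 test satisfies both signs. If they run from the first raised value, they fall on days 7, 14, 21, 28 and 35, and day 28 separates the two lists. The protocol does not fix the anchor.

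**The case against.** **The pointer in section 6.1.** It names 6.3.1, whose title marks it as the liver stopping section. This stands in part, because it narrows the ambiguity. It does not say that 6.3 is superseded. Section 6.3 is itself an imperative, section 4.4 is the formal withdrawal section, and section 4.4.2 mentions transaminase and bilirubin rules without saying which.

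**The lists may be cumulative.** Every version is a set of reasons to discontinue and none orders treatment to continue. Sections 4.4 and 6.3.1 also let the investigator stop for unacceptable risk. Read as a union, all four patients would stop. So it would go too far to infer that any section requires a patient to be kept on drug. But the documents nowhere say that the lists are cumulative, and 4.4 and 6.3.1 each introduce theirs as four conditions.

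**Sections 4.4 and 6.3.1 are nearly the same rule.** This stands. They differ only in strict against non-strict signs, which should be checked in the source protocol. A reader might speak of three materially different rules, but the text supports two versions plus boundary differences. The conflict with 6.3 lies in whole criteria and does not depend on a sign.

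**One centre is in charge.** Treatment starts at one centre and the Principal Investigator is responsible for safety. This lowers the chance of divergent readings but does not supply a single rule.

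**Conclusion.** The individual liver discontinuation criteria conflict between section 6.3 and the list in 4.4 and 6.3.1, on four features: progression, direct bilirubin, the stand-alone ALT limit and rash. The size is shown by the opposite answers for the four constructed patients. How often such patients would occur cannot be estimated from the documents. The boundary differences between 4.4 and 6.3.1 are minor, but one such patient among 15 could decide the 33% stop.

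Three stronger readings are not supported:

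- A reader might infer that the conflict with 6.3 itself changes the 33% count. Both statements of that rule are worded on 4.4 or 6.3.1, and neither counts the 6.3 criteria. Only boundary patients move it.
- A reader might infer a fixed delay of weeks between stopping under one section and another, for example day 28 under 4.4 against day 35 under 6.3.1. That depends on how the weekly tests are anchored after the confirmatory repeat, which the protocol leaves open.
- A reader might see a contradiction between the ALT entry limit of 2.5 times ULN and the restart limit of about 1.5 times ULN. Entry and discretionary re-exposure after a liver stop are different situations, so the two limits need not match.

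Nothing here judges which liver criteria are clinically right.

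**What to change.** Reconcile sections 4.4, 6.3 and 6.3.1 into one individual liver discontinuation and restart rule. Print it once, and replace the other versions with a cross-reference. Point sections 4.4.2 and 6.1 to it as well. State each comparison sign once, define progression if that criterion is kept, and say from which test the four weeks and the weekly retests are counted. Word the 33% study rule, wherever it appears, on that single definition. The sponsor must choose which criteria govern.

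The cost is a wording amendment, with no change to sample size, visits or analyses. Any liver discontinuations already recorded should be listed with the section and criterion applied, so that the count can be reproduced.
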